In this pilot study we will test the hypothesis that:

- 1) Guaifenesin use over a period of 14 days improves subjective nasal complaints in pediatric patients with chronic rhinitis and nasal congestion, as measured by the SN-5 survey compared to use of placebo.
- 2) There will be an observed improvement in nasal volume and cross-sectional area following use of guaifenesin, measured objectively using acoustic rhinometry compared to use of placebo.
- 3) Following treatment with guaifenesin, nasal secretions will have more favorable mucociliary and sneeze clearability compared to use of placebo.
- 4.) Children that respond and those that do not respond to guaifenesin therapy will show significant differences in mucus characteristics and mucociliary clearance.

Materials and Methods

Study Design

This is a 14-day, randomized, placebo-controlled, parallel group, masked clinical trial of oral guaifenesin for the therapy of CRS in 36 children between the ages of 7 and 18 years. A 2:1 ratio of subjects on active medication to placebo will be used. Before starting the study, this study will be approved by the Virginia Commonwealth University Institutional Review Board for human research. Study subjects will be assigned a unique coded identifier and all information will be entered into an Excel database in a password-protected computer, to which only the investigators have access. There is minimal risk to the child in acoustic rhinometry measurements, collecting nasal secretions, and completing the SN-5 surveys.

Subject Recruitment

We will enroll 36 subjects from the pediatric otolaryngology clinic at the Virginia Commonwealth University Medical Center in a 2:1 ratio of active medication to placebo. The subjects will be between the ages of 7 and 18 years at the time of the study. They will be identified during routine clinical evaluation for CRS as defined as chronic rhinitis and nasal stuffiness of at least 3 months duration. Informed consent will be obtained from the subject's parent or legal guardian and assent will be obtained from the study subjects. Given our clinic volume we anticipate that it will take 12 months to complete subject enrollment.

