After informed consent is obtained, a medical history will be obtained, including demographic data of personal or family history of allergies, asthma, nasal or sinus disease, exposure to tobacco smoke, prior medication history and other associated conditions. A head and neck physical examination will be performed, including a thorough rhinoscopic examination. We will determine nasal patency both by direct visualization and scoring and by acoustic rhinometry pretreatment and at post treatment follow-up, using the mean of three consecutive measurements. Secretions will be collected from the middle meatus pre and post treatment using the Jun-Tym-Tap. The SN-5 questionnaire will be completed at two baseline visits and after completion of the study.

The subject will be given a 14- day course of either guaifenesin or matched placebo to be taken orally three times daily according to following age-matched dosages: children aged 7-11 years old will receive guaifenesin 200 mg TID, while children older than 12 will receive guaifenesin 400 mg TID. Randomization of medication use will be carried out by a study participant not involved in the direct care of the patient. A 2:1 ratio of subjects on active medication to placebo will be used. After two weeks, the subject will return for data collection including nasal examination, SN-5, acoustic rhinometry, and collection of nasal secretions. Subjects that do not return for their follow up visit will be contacted to schedule repeat examination.

Data Analysis

Power calculation

The primary outcome variable will be changes in the SN-5 questionnaire score. It has been reported that the mean score in children with CRS is 3.8 with a standard deviation of 1.0 and a temporal effect size of standard therapy equal to 0.88¹¹. Thus assuming a normal distribution of results, using a paired 2-tail test to evaluate pre and post treatment outcome with an α error probability of 0.05 and a β (power) to detect a change of 0.88 at 80%, the critical t is 2.1788 yielding a sample size of 13 subjects per group¹⁷.

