We will also compare pre and post treatment nasal patency scores based upon subjective direct visualization score of % obstruction by a single investigator and objective mean acoustic rhinometry values, and pre- and post treatment mucus biophysical properties. Collected data will be used to evaluate the outcome measures most predictive of therapeutic response. We will compare responders to non-responders to see if there are factors in the history, physical examination, demographics (e.g. tobacco smoke exposure), or baseline measurement that predict response to guaifenesin. These pilot data will be used to develop a focused controlled prospective study of children and adults most likely to respond to oral guaifenesin.

References

- 3.) Bailey BJ and JT Johnson. Head & Neck Surgery – Otolaryngology: Fourth Edition. Lippincott Williams & Wilkins. 2006:vol 1, 405-416.

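### The responder versus non-responder comparison splits a numeric outcome and gives up about a third of the information in a 24-child arm; the continuous SN-5 change should be the main analysis

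*Protocol*

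**What the plan says.** The Power calculation part of the Data Analysis section sets the primary endpoint: "The primary outcome variable will be changes in the SN-5 questionnaire score". The SN-5 is completed at two baseline visits and again after treatment (Study Protocol section), so each child who returns has a numeric change.

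Two places use a yes/no label instead. Hypothesis 4, in the list after the Introduction, predicts: "Children that respond and those that do not respond to guaifenesin therapy will show significant differences in mucus characteristics". The last paragraph of Data Analysis applies the same split to predictors: "We will compare responders to non-responders to see if there are factors in the history, physical examination, demographics". It adds that the pilot results will guide the design of a later study in those most likely to respond. Neither place names the measure or cut-off that makes a child a responder.

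The SN-5 section quotes a test-retest reliability of 0.70 from one cited study. The Power calculation quotes, from another, that "the mean score in children with CRS is 3.8 with a standard deviation of 1.0".

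**The concern.** Cutting a numeric change into two groups treats a child just above the cut like one far above it, and unlike one just below it. That costs power whatever cut is used, so no definition supplied in a statistical analysis plan would remove the loss. The outcome is also measured with error, so some children fall on the wrong side of the cut, and real differences in mucus properties or baseline factors between the two groups shrink.

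At stake are a named hypothesis and the evidence meant to choose the population of the next study, drawn from a small number of treated children.

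**Working it through.** **Inputs from the protocol.** SN-5 SD 1.0, effect size 0.88, two-sided α 0.05, power 80%, 13 per group (Power calculation); test-retest R 0.70 (SN-5 section); total of 36 ("We will enroll 36 subjects from the pediatric otolaryngology clinic") at 2:1, so 36 × 2/3 = 24 on guaifenesin.

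**Assumptions not in the protocol.** Response is read from the SN-5 change; SD of observed change 0.8 to 1.2; mean change 0.44 or 0.88; cut-offs 0.5, 0.88 and 1.0; correlation of a predictor with observed change 0.3 to 0.6; normal distributions.

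**1. The plan's own figure.** For a paired t-test with standardised effect 0.88, n = 13 gives 12 degrees of freedom, critical t 2.1788, noncentrality 0.88 × √13 = 3.17 and power 0.829. With n = 12, power is 0.792. The stated result, "the critical t is 2.1788 yielding a sample size of 13 subjects per group", reproduces. Reading 0.88 as score points with SD 1.0 implies an SD of change of 1.0, the central case below.

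**2. Information kept by a split.** If a proportion p are called responders, the share kept is φ(z_p)² / [p(1 − p)]. At p = 0.5 this is its maximum, 2/π = 0.637. Over the cut-offs and SDs tried it runs from 0.53 to 0.64. So 24 children count as 24 × 0.53 = 13 to 24 × 0.64 = 15.

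**3. Power in 24 children.** Simulated with a continuous predictor and a 50/50 split:

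| Correlation with observed change | Continuous change | Split |
|---|---|---|
| 0.3 | 30% | 20% |
| 0.4 | 51% | 33% |
| 0.5 | 73% | 50% |
| 0.6 | 90% | 70% |

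Repeat runs differ by about one percentage point. A 30/70 split is worse: about 45% at a correlation of 0.5.

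**4. Measurement error.** Error SD of one score = 1.0 × √(1 − 0.70) = 0.55. Error SD of a single pre/post change = √(2 × 0.30) = 0.77. With an SD of change of 1.0, the variance of true change is 1.00 − 0.60 = 0.40, so the reliability of the *change* is 0.40, not 0.70. At SDs of change of 0.8 and 1.2 it is (0.64 − 0.60)/0.64 = 0.06 and (1.44 − 0.60)/1.44 = 0.58.

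**5. Children mislabelled** (true and observed change on opposite sides of the cut):

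| Mean change | SD of change | Cut 0.5 | Cut 0.88 | Cut 1.0 |
|---|---|---|---|---|
| 0.88 | 0.8 | 31.6% | 42.0% | 40.6% |
| 0.88 | 1.0 | 25.5% | 28.2% | 27.9% |
| 0.88 | 1.2 | 21.0% | 22.3% | 22.1% |
| 0.44 | 0.8 | 41.7% | 29.1% | 24.2% |
| 0.44 | 1.0 | 28.2% | 24.7% | 22.7% |
| 0.44 | 1.2 | 22.3% | 20.6% | 19.5% |

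The range is about 20% to 42%. In the central case (mean 0.88, SD 1.0) at cuts of 0.5 and 0.88, that is 24 × 0.255 = 6 to 24 × 0.282 = 7 children.

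**6. What this noise does to the continuous analysis.** It multiplies a correlation with true change by the square root of the reliability of the change, √0.40 = 0.63 in the central case. An observed correlation of 0.5 therefore needs a true one of 0.5/0.63 = 0.79. The losses in step 3 come on top of this, because those correlations already refer to observed change.

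**The case against.** **The basis of response is an inference.** Data Analysis also lists a visual obstruction score, acoustic rhinometry and mucus properties. This stands, so the SN-5 basis is given as an assumption. The SN-5 is the natural reading because it is the primary outcome and the yardstick in hypothesis 1. Splitting any other continuous measure would also lose information, but the mislabelling figures would not carry over.

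**No cut-off is stated.** A reader might infer that the cut would be chosen after seeing the data. Nothing in the protocol says so, and the definition may sit in a statistical analysis plan that is not shown. That is not part of this point.

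**Noise affects both analyses.** A reader might take the reliability of 0.70 as proof that the split is at fault, or conclude that labels would be mostly error. Neither follows. The noise also weakens the continuous analysis, as step 6 shows, and under the assumptions tried most children are still labelled correctly.

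**The error SD joins two cited sources.** The SD and the reliability may come from different populations, and the retest interval is not given. If the two baseline scores were averaged, the error SD would be √(0.30/2 + 0.30) = 0.67. The mislabelling range is therefore conditional. The information loss in steps 2 and 3 does not use the reliability.

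**The comparison is exploratory and two groups suit its aim.** This is a pilot, and the wish to identify likely responders makes a split convenient. That limits the severity. It does not make the split the better method, since a continuous analysis addresses the same aim with more information.

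**Conclusion.** The point holds as a modest improvement to a secondary, exploratory analysis. The protocol fixes a two-group form where a numeric outcome is already collected. If response is read from the SN-5 change, the split keeps at most about 64% of the information and takes 10 to 23 percentage points off the power to detect a predictor in the 24 treated children (30 − 20 at a correlation of 0.3; 73 − 50 at 0.5). With SD 1.0 and R 0.70 both applying to this population, about a fifth to two fifths of children would be mislabelled, depending on the cut and the SD of change.

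The gain from keeping the change continuous should not be oversold: at a correlation of 0.3 the continuous analysis has only about 30% power. Nor do these results touch the primary comparison or the sample size.

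**What to change.** Reword hypothesis 4 to predict that mucus characteristics and mucociliary clearance are associated with the size of the SN-5 change. In the last paragraph of Data Analysis, make the main analysis the association of each mucus, history, examination, demographic or baseline factor with the continuous SN-5 change, adjusted for baseline SN-5. Keep any responder table as description only, with one cut-off fixed before unmasking.

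The cost is a change of wording. No further data, visits or children are needed. The one drawback is that a slope is slightly harder to present than a comparison of two groups, which the descriptive table can offset.

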Children with immunodeficiency, cystic fibrosis, acute or subacute symptoms, signs of bacterial infection, and/or those who are unable to cooperate with testing will be excluded. Children with documented use of the study medication in the month before evaluation and during period of symptoms will also be excluded.

Parents of the subjects will complete the SN-5 questionnaire as described below, at initial evaluation and again during a lead-in phase three days later to ensure stability of symptoms. Patients with an improved score will be excluded.

The Sinus and Nasal Quality of Life Survey (SN-5)

The Sinus and Nasal Quality of Life Survey (SN-5) is a validated and reliable questionnaire designed to score five areas of impact from sinonasal dysfunction (SN-5) in patients 1 year to 18 years of age^{9,10}. Parents assess the impact of infection on nasal symptoms, emotion, and activity on a scale of worsening symptoms scored 1 through 7 to provide a quantifiable score capable of comparing both disease severity and the impact of interventions on subjective complaints. It has been shown as a responsive measure of health-related quality of life

for children with persistent sinonasal symptoms, suitable for use in outcomes studies and routine clinical care. Kay et al showed SN-5 test-retest reliability with an R value of 0.70⁹. Terrell et al demonstrated that the SN-5 correlated to disease severity as measured by the Lung-MacKay CT scan score¹¹.

Acoustic rhinometry

Acoustic rhinometry is used to measure cross-sectional volume of the nasal cavity allowing the calculation of nasal volume. Audible reflected sound waves are painlessly introduced through nasal adaptors into the nasal passages allowing the production of area-distance graphs. As the acoustic rhinometer is calibrated to a standard nose, accurate results can be obtained with good test-retest reliability^{12,13}.

Analysis of nasal secretions

Secretion collection

Collection and analysis of nasal secretions will be performed under direct vision at the time of rhinologic assessment. These will be collected using the Jun-Tymp-Tap (Xomed, Jacksonville, FL) as previously described¹⁴.

Mucociliary clearability

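### If response is read from SN-5 change, baseline SN-5 is mathematically tied to it and tends to look like a predictor of response even when no child changes

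*Protocol*

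**What the plan says.** Under Power calculation the protocol states: "The primary outcome variable will be changes in the SN-5 questionnaire score". The last paragraph of Data Analysis then sets out the predictor search: "We will compare responders to non-responders to see if there are factors in the history", the physical examination, demographics, or a "baseline measurement that predict response to guaifenesin". The results are to be used to "develop a focused controlled prospective study of children and adults most likely to respond to oral guaifenesin".

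SN-5 is itself a baseline measurement. Parents complete it "at initial evaluation and again during a lead-in phase three days later" (Subject Recruitment), and children whose score improves between those two occasions are excluded. Study Protocol confirms two baseline completions and one after treatment. The SN-5 section cites a test-retest reliability of 0.70 and describes a scale from 1 to 7 on which higher is worse.

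The text does not say what makes a child a responder or which of the two baselines enters the change. It does not say that predictors will be compared between the guaifenesin and placebo arms.

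**The concern.** A change score contains the baseline. If a parent happens to rate a child as worse than usual at baseline, that rating error raises the baseline score. It also raises the improvement computed from it, because the next rating will on average be closer to the child's usual level. High baseline and apparent response are then associated through arithmetic, with no drug effect and no change in any child.

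The search ranks candidate predictors against each other, and its stated use is to pick the population of the next study. Baseline SN-5 would enter with an advantage that smoke exposure, history and mucus properties do not have when response is SN-5 change. Severity could then help decide who is studied next because of an artefact.

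**Working it through.** **The protocol's own figure.** "using a paired 2-tail test to evaluate pre and post treatment outcome" with "an α error probability of 0.05" and an effect of 0.88 reproduces. With 12 children the power is 0.792. With 13 the critical t is 2.1788 and the power is 0.829, so 13 per group is correct for that test. The sample size is not at issue here.

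**Inputs from the protocol.**
- Spread: "the mean score in children with CRS is 3.8 with a standard deviation of 1.0".
- Test-retest reliability R = 0.70.
- 36 children at 2:1, so 36 × 2/3 = 24 on guaifenesin and 12 on placebo.
- Lead-in exclusion of children whose second score improved.

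**Assumptions not in the protocol.** Response is SN-5 change from baseline. Scores are continuous, errors are normal and independent between occasions, and no child truly changes. Responders are compared with non-responders among the 24 treated children. R is varied up to 0.9 and, for the formula, down to 0.5.

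**Formula, without the exclusion.** Write baseline B = T + e1 and final score P = T + e2, with improvement B − P.
- With SD 1.0 and R = 0.70, the variance of T is 0.70 and each error variance is 0.30.
- Covariance of B with B − P = variance of e1 = 0.30.
- Variance of B − P = 0.30 + 0.30 = 0.60.
- Correlation = 0.30 / (1.0 × √0.60) = 0.387, which in general is √((1 − R)/2).
- At R = 0.5 this is √0.25 = 0.50. At R = 0.9 it is √0.05 = 0.22.
- Slope = 0.30/1.0, so a child one point above the mean shows an expected false improvement of 0.30 points.

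**Simulation, sets of 24 treated children.** Responders are split at the median change, and baseline SN-5 is compared by a t-test at a nominal 5%. With the exclusion applied, change is taken from the lead-in score.

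| R | Lead-in exclusion | Correlation of baseline with improvement | Comparison rejects |
|---|---|---|---|
| 0.70 | no | 0.39 | about 31% |
| 0.70 | yes | 0.30 | about 20% |
| 0.80 | yes | 0.24 | about 14% |
| 0.90 | yes | 0.17 | about 9% |

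The result does not depend on the median split. With fixed responder cut-offs of 0, 0.5 or 0.88 points at R = 0.70, the rejection rate is 18–21% with the exclusion and 23–32% without it. With the exclusion and the 0.5 cut-off, 52% of the top baseline third count as responders against 27% of the bottom third.

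**Possible remedies at R = 0.70, still with no true change.**
- Baseline-by-arm comparison: the artefact is the same in both arms and cancels. It rejected in 5.2% of simulated trials.
- Initial score as predictor, change from the lead-in score: correlation 0.00 and about 5% rejections without the exclusion; 0.14 and 8–10% with it. If the errors of the two baselines are correlated at an assumed 0.3 to 0.5, about 0.22 to 0.27 and 13–26% remain.
- Mean of the two baselines used as both predictor and starting point: the correlation falls only to 0.24, so averaging does not solve it.

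**Precision of the arm comparison, without the exclusion.** The residual SD of change given baseline is √(0.60 × (1 − 0.387²)) = 0.71. The standard error of the difference between the two arms' slopes is about 0.71 × √(1/23 + 1/11) = 0.26. That is nearly as large as the artefact slope of 0.30.

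**The case against.** The strongest objection is that the protocol does not state this error. No responder rule is given, SN-5 is not named among the predictors, and a rule based on the final score alone, or on the other baseline, would not create the coupling in this form. Responder rules are commonly left to a statistical analysis plan, which is not available here. This stands to the extent that the point must be conditional and the missing definition is no fault in itself. It does not remove the point: the protocol admits baseline measurements as predictors, its primary outcome is SN-5 change, and nothing in it points to a different basis for response.

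Three stronger readings are tempting, and the document supports none of them.
- *A high baseline will appear to predict response.* The bias is certain in expectation, but a significant finding is not. A 48% rejection rate can be obtained, but only by correlating baseline with continuous change in a cohort without the lead-in exclusion. The protocol plans a responder comparison and applies the exclusion, so about 20% is the matching figure. About four pilots in five would show no significant association.
- *All baseline measurements are affected.* If response is SN-5 change, only baseline SN-5 is a component of it.
- *The same size applies to rhinometry or mucus if response is read from those.* The mechanism would apply to that measure's own baseline, but the protocol gives no reliability figure for either. It also uses the mean of three rhinometry readings and takes three transport measurements. The size is unknown.

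It can also be said that this is one candidate in an exploratory search within a pilot. That limits the weight of the point. Choosing the next study's population is, however, the stated use of these data.

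**Conclusion.** The point holds in conditional form. If response is SN-5 change from baseline, the planned comparison tends to show higher baseline SN-5 in responders when no child has changed. At R = 0.70 with the lead-in exclusion, the correlation is about 0.30 and the false-positive rate about 20%, four times the nominal 5%. At R = 0.9 the rate is about 9%. This rests on normal independent errors, 24 treated children and no true change. The primary outcome and the sample size are untouched. A reader might infer that the protocol commits to a biased rule or that a false finding is inevitable; the text supports neither.

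**What to change.** 1. When baseline SN-5 is examined as a predictor, test whether its association with SN-5 change differs between the guaifenesin and placebo arms.
2. As a supporting analysis, use the initial-evaluation score as predictor and compute change from the lead-in score.
3. State that baseline severity will not be carried into the next study's population on a treated-arm, same-baseline association alone.
4. If response is read from rhinometry or mucus, treat that measure's own baseline in the same way: compare it between arms rather than within the treated arm only.

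The cost is analysis wording. Both SN-5 baselines and the placebo arm already exist, so no visits, children or measurements are added. The arm comparison will be imprecise with 12 placebo children, and failing to find a difference will settle little. The split-baseline analysis is slightly noisier, leaves a correlation of about 0.14 after the lead-in exclusion, and leaves more if the two baseline errors are correlated. It should therefore support the arm comparison and not replace it.
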